12.5 ADVERSE EVENTS / SERIOUS ADVERSE EVENT CAUSALITY ASSESSMENT

The Investigator must also assess the relationship of any adverse event to the use of study drugs (whether none, one, or both), based on available information, using the following guidelines:

- **Not Related:** Clear-cut temporal and/or mechanistic relation to a cause other than the study drug(s).
- **Doubtful:** There is no reasonable possibility that the event is related to the study drug(s) but a definite cause cannot be ascertained.
- **Possible:** There is still a reasonable possibility that the cause of the event was the study drug(s) but there exists a more likely cause of the event such as complications of progressive disease.
- **Probable:** The most likely cause of the event is the study drug(s) but other causes cannot be completely excluded.

- **Definite:** Clear cut temporal and/or mechanistic relation to the study drug(s). All other causes have been eliminated. Events classified as definite will often be confirmed by documenting resolution on discontinuation of the study drug and recurrence upon resumption.

12.5.1 RECORDING OF ADVERSE EVENTS

All adverse events of any subject during the course of the study will be reported on the case report form, and the investigator will give his or her opinion as to the relationship of the adverse event to study drug treatment (i.e., whether the event is related or unrelated to study drug administration – either ublituximab, umbralisib, venetoclax, ibrutinib). If the adverse event is serious, it should be reported as soon as possible and no greater than 24 hours to the sponsor or designee. Other untoward events occurring in the framework of a clinical study are also to be recorded as AEs (i.e., AEs that occur prior to assignment of study treatment that are related to a protocol-mandated intervention, including invasive procedures such as biopsies, medication washout, or no treatment run-in).

All AEs regardless of seriousness or relationship to ublituximab, umbralisib, venetoclax or ibrutinib from Cycle 1/Day 1 until 30 calendar days after discontinuation or completion of either protocol-specific treatment as defined by the protocol for that subject, are to be recorded on the eCRF.

12.5.2 ABNORMAL LABORATORY VALUES AND VITAL SIGNS

The reporting of abnormalities of vital signs as adverse events should be avoided. Abnormalities of vital signs should not be reported unless any criterion for an SAE is fulfilled, the vital signs abnormalities cause the subject to discontinue study treatment, or the investigator insists that the abnormality should be reported as an AE. Abnormal laboratory results should be noted in the eCRF as an adverse event if they are associated with an overdose, require or prolong inpatient hospitalization, or are otherwise considered clinically significant by the investigator. If an abnormal laboratory value or vital sign is associated with clinical signs and/or symptoms, the sign or symptom should be reported as an AE, and the associated laboratory value or vital sign should be considered additional information that must be collected in the relevant eCRF. If the laboratory abnormality is a sign of a disease or syndrome, only the diagnosis needs to be recorded on the SAE Report Form or AE eCRF.

Clinical Laboratory Results will be summarized. Summary statistics for actual values and for changes from baseline will be tabulated for laboratory results by scheduled visit. Subjects with laboratory values outside of the normal reference range at any post-baseline assessment will be summarized and graded per NCI CTCAE Version 5.0 when applicable. Subject incidence of abnormal laboratory results will be summarized by treatment group and maximum grade for each abnormal laboratory finding.

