7 STUDY ASSESSMENTS AND TREATMENT SCHEDULES

7.1 STUDY ASSESSMENT AND TREATMENT SCHEDULE - INITIAL TREATMENT

Cycle=28 days	Screen	Cycle 1 ¹				Cycle 2-6 ²	C9 and every 3 cycles through C24 ³	EOS*
Procedure/Days	-28-1	D1	D2	D8	D15	Day 1	Day 1	
Medical History	X							
Rai Staging	X							
ECOG	X	X				X	X	X
Physical Examination	X	X				X	X	X
Vital Signs⁴	X	X	X	X	X	X	X	X
12-Lead EKG	X							
Hematology	X	X	X	X	X	X	X	X
Chemistry	X	X	X	X	X	X	X	
Coagulation Studies	X	X				X	X	
HCV, HBV, CMV⁵	X							
CMV surveillance⁶						C3&6	C9, 12, 15, etc.	
PB MRD⁷	X					X	X	
β₂-microglobulin	X							
Pregnancy Test⁸	X					X	X	
Response assessments¹⁰	X					C3 & C6	C 12, 18 & C24	
AE Evaluation	X	X	X	X	X	X	X	X
Con Meds	X	X	X	X	X	X	X	X
Ublituximab		X	X	X	X	X	X	
Umbralisib						Daily until confirmed U-MRD ¹¹		
Cohort A: Ibrutinib						Daily until confirmed U-MRD ¹¹		
Cohort B: Venetoclax						Daily until confirmed U-MRD ¹¹		
Cohort C: Acalabrutinib						Every 12 hours until confirmed U-MRD ¹¹		

¹ Treatment Administration +/- 1 day window after cycle 1 day 1. Physical Exam, Vital Signs, ECOG PS, Hematology and Serum Chemistry visit days have - 1 day window. All assessments must be completed prior to dosing.

² Treatment Administration +/- 3 day window. Physical Exam, Vital Signs, ECOG PS, Hematology and Serum Chemistry visit days have a - 3 day window during Cycles 2 through 6.

³ Treatment Administration +/- 7 day window. Physical Exam, Vital Signs, ECOG PS, Hematology and Serum Chemistry visit days have a - 7 day window for all cycles after cycle 6

⁴ Vital signs to include temp, BP, HR, respirations and weight (weight only at baseline).

⁵ Serum Virology to include HBsAg, HBc antibody, HCV antibody, CMV IgG and IgM. If HBc antibody is positive, the subject must be evaluated for the presence of HBV DNA by PCR - See Appendix D. If the subject is CMV IgG or IgM positive, the subject must be evaluated for the presence of CMV DNA by PCR. If subject is HCV positive, evaluate HCV RNA.

⁶ CMV surveillance by PCR every 3 cycles while receiving study treatment. In addition, a final CMV test by PCR should be done upon treatment discontinuation if not already done within previous 3 months.

⁷ For initial treatment, MRD analysis (central lab) in peripheral blood (PB) performed within 30 days prior to Cycle 1/Day 1. MRD analysis in PB during cycles 3, 6, 9, 12, 15, 18, 21, and 24. U-MRD in PB during initial treatment must be confirmed in PB 4 approximately weeks later.

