- **Infections and Infestations:** bronchitis, cellulitis, clostridium difficile colitis, enterocolitis infectious, oral candidiasis, oral herpes, otitis media, pneumonia, pneumonia streptococcal, rhinovirus infection, sepsis, sepsis syndrome, sinusitis, skin infection, upper respiratory tract infection, urinary tract infection
- **Injury, Poisoning and Procedural Complications:** wound
- **Investigations:** alanine aminotransferase increased, aspartate aminotransferase increased, blood alkaline phosphatase increased, blood creatinine increased, computerised tomogram thorax abnormal, immunoglobulins decreased, weight decreased
- **Metabolism and Nutrition Disorders:** dehydration, failure to thrive, hyperglycaemia, hyperuricaemia, hypokalaemia, hypophosphataemia
- **Musculoskeletal and Connective Tissue Disorders:** joint swelling, muscle spasms, muscular weakness, myalgia, pain in extremity
- **Nervous System Disorders:** dizziness, dysgeusia, headache, lethargy, sinus headache, somnolence
- **Psychiatric Disorders:** agitation, anxiety
- **Renal and Urinary Disorders:** micturition urgency, renal failure, renal failure acute
- **Reproductive System and Breast Disorders:** scrotal cyst, semen discolouration
- **Respiratory, Thoracic and Mediastinal Disorders:** choking, cough, dysphonia, dyspnea, epistaxis, hypoxia, oropharyngeal pain, pneumonitis, productive cough, sinus congestion
- **Skin and Subcutaneous Tissue Disorders:** alopecia, cold sweat, dermatitis acneiform, dermatitis bullous, dry skin, ecchymosis, pruritus, rash, maculo-papular, rosacea, urticaria
- **Vascular Disorders:** hypertension

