- **Ear and Labyrinth Disorders:** tinnitus, vertigo

- **Eye Disorders:** vision blurred
- **Gastrointestinal Disorders:** abdominal distension, abdominal pain, constipation, dyspepsia, gastroesophageal reflux disease, mouth ulceration, odynophagia, upper gastrointestinal haemorrhage
- **General Disorders and Administration Site Conditions:** asthenia, chills, feeling jittery, influenza like illness, oedema peripheral, pain
- **Immune System Disorders:** pemphigus
- **Infections and Infestations:** bronchitis, cellulitis, lung infection, oral candidiasis, oral herpes, paronychia, pneumonia, respiratory tract infection, sepsis, septic shock, sinusitis, skin candida, streptococcal bacteraemia, upper respiratory tract infection, urinary tract infection, varicella
- **Injury, Poisoning and Procedural Complications:** contusion
- **Investigations:** alanine aminotransferase increased, aspartate aminotransferase increased, blood alkaline phosphatase increased, blood bilirubin increased, coagulation time prolonged, lipase increased, weight decreased
- **Metabolism and Nutrition Disorders:** decreased appetite, hyperglycaemia, hypertriglyceridaemia, hypoalbuminaemia, hypocalcaemia, hypokalaemia, hypophosphataemia
- **Musculoskeletal and Connective Tissue Disorders:** arthritis, bone pain, muscle spasms, muscle tightness, musculoskeletal pain, myalgia, neck pain, pain in extremity
- **Neoplasms Benign, Malignant, and Unspecified:** basal cell carcinoma
- **Nervous System Disorders:** amnesia, headache, lethargy, mental impairment, neuropathy peripheral, subdural hygroma, syncope, tremor
- **Psychiatric Disorders:** anxiety, confusional state, insomnia
- **Renal and Urinary Disorders:** dysuria, haematuria, pollakiuria, polyuria
- **Reproductive System and Breast Disorders:** penile blister
- **Respiratory, Thoracic and Mediastinal Disorders:** cough, dysphonia, dyspnoea, haemoptysis, lung infiltration, oropharyngeal pain, pleural effusion, pneumonitis, pulmonary oedema
- **Skin and Subcutaneous Tissue Disorders:** alopecia, blister, butterfly rash, dermatitis bullous, dry skin, ecchymosis, eczema, epistaxis, onychoclasia, petechiae, pruritus, pruritus generalized, rash generalized, rash macular, rash maculo-papular
- **Vascular Disorders:** flushing, hypertension

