11.1 SAFETY ANALYSES

Safety evaluations will be based on the incidence, intensity, and type of adverse events, as well as on clinically significant changes in the subject's physical examination, vital signs, and clinical laboratory results. Safety analyses will be performed using the safety population. Safety variables will be tabulated and presented by the treatment regimens received. Exposure to study treatment and reasons for discontinuation of study treatment will also be tabulated.

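### Section 12.5.2 discourages AE reporting of vital-sign abnormalities, so some non-serious, asymptomatic blood-pressure events may be undercounted, and no specified blood-pressure summary offsets this

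*Combined protocol and SAP*

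**What the plan says.** Section 12.5.2 sets a default against reporting: "The reporting of abnormalities of vital signs as adverse events should be avoided". It continues: "Abnormalities of vital signs should not be reported unless any criterion for an SAE is fulfilled, the vital signs abnormalities cause the subject to discontinue". That second exception concerns stopping the trial drugs. A third is worded "or the investigator insists that the abnormality should be reported as an AE". For abnormalities with symptoms the rule is: "If an abnormal laboratory value or vital sign is associated with clinical signs and/or symptoms, the sign or symptom should be reported as an AE". The blood-pressure value is then kept as supporting information.

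The same section treats laboratory results differently. They become AEs if linked to an overdose, if they lead to or prolong an inpatient stay, or if the investigator considers them clinically significant. They also have a defined analysis: actual values and change from baseline by visit, CTCAE grading, and incidence by maximum grade.

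The Safety Analyses section (numbered 11.1, placed after 11.6) bases the safety evaluation on AEs and on clinically significant changes in "physical examination, vital signs, and clinical laboratory results". It says that safety variables will be tabulated by regimen received.

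Blood pressure is collected throughout. Footnote 4 of the schedule in 7.1 reads "Vital signs to include temp, BP, HR, respirations and weight (weight only at baseline". Hypertension appears among the common events (1% to <10%) in 9.3 for ublituximab + umbralisib ("Vascular Disorders: hypertension") and in 9.4.1 for the ibrutinib triplet ("flushing, hypertension").

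**The concern.** Safety and tolerability are a named secondary objective, and the AE tables in 12.4 count only what sites have recorded. A rule that starts from not reporting can lower the recorded frequency of one kind of event. Because the last exception depends on an investigator pressing the point, the loss may also differ between sites. Blood pressure is where this matters most in these documents: it is measured at nearly every visit, and hypertension is already listed as at least possibly related to the ublituximab + umbralisib backbone that all three cohorts receive. If AE counts run low, a defined summary of the measured values would be the natural safeguard, and none is specified.

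**Working it through.** The plan states no figure on this point, so the check compares the sections and then gives an illustration.

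**1. Two tests within 12.5.2.** For a laboratory value, the investigator's judgment of clinical significance is enough. For a vital sign, that judgment is not among the listed conditions, and the investigator has to override a default. The treatment exception covers discontinuation; it does not mention interruption.

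**2. Against the general rules.** Section 12.1 says that any unfavorable, unintended sign can be an AE and leaves the determination to the investigator. Section 12.5.1 has all AEs recorded on the eCRF whatever their seriousness or relationship to treatment. The synopsis says that all AEs will be reported and evaluated with CTCAE v5.0. The default in 12.5.2 does not fit with these.

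**3. Which events are exposed.** Start from all blood-pressure abnormalities and remove those with another route to the AE form:
- those that meet an SAE criterion, including the medically important category in 12.2;
- those that lead to discontinuation of treatment;
- those with symptoms, where the symptom is the AE (and is counted under the symptom's own term);
- those named as a recognized condition under 12.9;
- worsening of a pre-existing condition under 12.9.5;
- those on which the investigator insists.

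What remains is new, non-serious, asymptomatic, compatible with continued treatment, and not written down as a diagnosis. Sites can differ on the last step. Section 12.9 starts from AEs, which 12.5.2 tells sites not to create from vital signs, and the diagnosis sentence in 12.5.2 refers only to laboratory abnormalities.

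**4. Whether the analysis compensates.** The Safety Analyses section names vital signs and promises tabulation. It gives no blood-pressure statistic, threshold, grade or time point, and does not define clinical significance. The detailed summaries in 12.5.2 are for laboratory results only.

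**5. Whether the data exist.** Vital signs are marked in all 8 columns of the 7.1 schedule and both columns of 7.2. In 7.3 there are 14 marks for 15 columns; long-term follow-up appears to be the one without.

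**6. Illustration of size.** Inputs: n = 28 per cohort (the synopsis gives up to approximately 28); true rate p across the listed band, with 10% as its upper limit; reporting fraction f, which is an assumption because the documents give none. The chance of at least one recorded hypertension AE is 1 − (1 − p·f)^28, and the expected number recorded is 28·p·f.

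| True rate p | f = 1 | f = 0.5 | f = 0.25 |
|---|---|---|---|
| 1% | 24.5% | 13.1% | 6.8% |
| 5% | 76.2% | 50.8% | 29.7% |
| 10% | 94.8% | 76.2% | 50.8% |

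Example: p = 5% and f = 0.5 give 1 − 0.975^28 = 50.8%. At p = 10% the expected recorded cases are 28 × 0.10 = 2.8 with full reporting, 1.4 at one half and 0.7 at one quarter.

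**The case against.** The strongest reply is that 12.5.2 restricts readings, not diagnoses. Hypertension is listed in 9.3 and 9.4.1 as a vascular disorder, 12.9 has a recognized condition named as such, 12.9.5 captures worsening of a pre-existing condition, some treated cases could qualify as medically important under 12.2, and the investigator can always have the event reported. If sites follow those routes, f is close to 1 and little is lost. This stands as a limit on the concern: a reader might infer that hypertension is kept off the AE form, and the documents do not support that. It does not remove the problem, because 12.5.2 never says that a diagnosis made from vital signs is exempt, and its default points the other way.

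A reader might also infer that no blood-pressure analysis is planned. That is too strong, since the Safety Analyses section includes vital signs and says safety variables will be tabulated. The fair criticism is that the content is unspecified.

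Three further inferences go beyond the documents. Hypertension is listed for ublituximab + umbralisib and for the ibrutinib triplet; it is not in the venetoclax table in 9.5.1, and no event list is given for the acalabrutinib triplet. Nothing shows that this trial's rate could not be compared with the earlier ones, because the AE-reporting rules behind those lists are not given. Infusion-related hypotension (8.3.1) is a weak example, since infusion related reaction is itself a listed AE.

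**Conclusion.** The concern holds in a limited form. Section 12.5.2 applies a stricter test to vital signs than to laboratory values and conflicts with 12.1 and 12.5.1. Followed as written, it may undercount one class of event: non-serious, asymptomatic blood-pressure abnormalities that do not stop treatment and are not recorded as a diagnosis. The undercount may vary by site, and no specified blood-pressure analysis would reveal it.

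The size cannot be established from the documents. The illustration rests on three assumptions: that the listed band is a fair guide to the true rate, that a cohort reaches 28, and that the reporting fraction lies between one quarter and full. The primary U-MRD endpoint is unaffected. The correction is worth making because safety is a secondary objective and the correction is cheap.

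**What to change.** Reconcile 12.5.2 with 12.1 and 12.5.1. Replace its first two sentences with the clinical-significance test that the section already applies to laboratory values, so that one rule covers both. Keep the rule on symptoms.

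In the Safety Analyses section, specify by cohort:
- change from baseline in blood pressure and heart rate by visit;
- worst post-baseline CTCAE v5.0 blood-pressure grade against baseline grade, stating which reading is baseline and how the grade is derived.

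Both use vital signs already collected, so no visit or procedure is added. The cost is protocol wording, a few more AE records, one extra table and possibly a higher reported hypertension rate.

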4.1 INCLUSION CRITERIA

1. Subjects with CLL who are currently receiving treatment with ibrutinib, acalabrutinib or venetoclax for greater than or equal to 6 months.
2. Minimal residual disease (MRD) positive (D-MRD) as determined by central lab performed during screening period.
 - a. For subjects receiving venetoclax: response assessment demonstrating stable disease, partial response, or complete response AND detectable MRD in the peripheral blood (central lab).
 - b. For subjects receiving ibrutinib or acalabrutinib: response assessment demonstrating stable disease, partial response or partial response with lymphocytosis, or complete response AND detectable MRD in the peripheral blood (central lab).
3. Adequate organ system function, defined as follows:
 - a. Absolute neutrophil count (ANC) $\geq 1,000/\text{mm}^3$ (μL) / platelet count $\geq 50,000/\text{mm}^3$ (μL). Growth factor to maintain these counts is permitted during screening period and throughout the conduct of the trial.
 - b. Total bilirubin ≤ 1.5 times the upper limit of normal (ULN), unless a diagnosis of Gilbert's syndrome or an autoimmune hemolytic anemia.
 - c. Alanine aminotransferase (ALT) and aspartate aminotransferase (AST) $\leq 2.5 \times \text{ULN}$ if no liver involvement or $\leq 5 \times \text{the ULN}$ if known liver involvement.
 - d. Calculated creatinine clearance $>30 \text{ mL/min}$ (as calculated by the modified Cockcroft-Gault formula, MDRD formula, or 24-hour urine CrCl).
4. ECOG performance status ≤ 2 .
5. Male or female ≥ 18 years of age.
6. Ability to swallow and retain oral medication.
7. Female subjects who are not of child-bearing potential (see Appendix B- Contraceptive Guidelines and Pregnancy), and female subjects of child-bearing potential who have a negative serum pregnancy test within 3 days prior to Cycle 1, Day 1. Female subjects of child-bearing potential, and male partners must consent to use a medically acceptable method of contraception throughout the study period and for 4 months after the last dose of ublituximab or umbralisib, and for at least 30 days after the last dose of ibrutinib, acalabrutinib or venetoclax.
8. Willingness and ability to comply with trial and follow-up procedures and give written informed consent.

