10.4 COMPLETE RESPONSE

To satisfy criteria for a CR, all of the following criteria must be met:

- No evidence of new disease
- ALC in peripheral blood of $<4 \times 10^9/L$
- Regression of all target nodal masses to normal size ≤ 1.5 cm in the LD
- Normal spleen and liver size

- Regression to normal of all nodal non-target disease and disappearance of all detectable non-nodal, non-target disease
- Peripheral blood counts meeting all of the following criteria:
 - ANC $>1.5 \times 10^9/L$ without need for exogenous growth factors (e.g., G-CSF)
 - Platelet count $\geq 100 \times 10^9/L$ without need for exogenous growth factors
 - Hemoglobin $\geq 110 \text{ g/L}$ (11.0 g/dL) without red blood cell transfusions or need for exogenous growth factors (e.g., erythropoietin)

Subjects who fulfill all the criteria for a CR but who have a persistent anemia, thrombocytopenia, or neutropenia or a hypocellular bone marrow that is related to prior or ongoing drug toxicity (and not to CLL) will be considered as a CR with incomplete marrow recovery (CRi).

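### The graded laboratory incidence table in Section 12.5.2 has no baseline-grade condition and no shift table is planned, so it mixes pre-existing with new abnormalities

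*Combined protocol and SAP*

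**What the plan says.** Section 12.5.2 plans three laboratory displays.

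- A continuous summary: "Summary statistics for actual values and for changes from baseline will be tabulated for laboratory results by scheduled visit".
- A graded summary of subjects: "Subjects with laboratory values outside of the normal reference range at any post-baseline assessment will be summarized and graded per NCI CTCAE Version 5.0", where grading applies.
- A count from that summary: "Subject incidence of abnormal laboratory results will be summarized by treatment group and maximum grade for each abnormal laboratory finding".

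The second and third carry no condition on the baseline value or grade. No shift table appears here or elsewhere in the protocol.

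The entry limits are in Section 4.1, criterion 3: ANC at least 1,000/mm³; platelets at least 50,000/mm³; ALT and AST up to 2.5 × ULN, or 5 × ULN with liver involvement; bilirubin up to 1.5 × ULN, waived for Gilbert's syndrome or autoimmune hemolytic anemia. No hemoglobin limit is listed. The counts may be supported: "Growth factor to maintain these counts is permitted during screening period and throughout the conduct of the trial". Criterion 1 requires at least 6 months on ibrutinib, acalabrutinib or venetoclax.

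Baseline is used elsewhere. Section 12.4 counts an event present before dosing as treatment-emergent if it worsens or is later judged related. Section 12.9.5 records a pre-existing condition as an adverse event only if it worsens. The safety analysis paragraph at the end of Section 11 refers to clinically significant changes in laboratory results.

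**The concern.** Safety and tolerability of the combinations is a secondary objective (Section 3.1). Cohorts are set by the drug the subject already takes (Section 6) and are evaluated separately, with no concurrent control. Each subject's own baseline is then the only reference for what changed after ublituximab and umbralisib were added.

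The graded incidence table does not use that reference. A subject who enters with a mildly low platelet count or an ALT of 2 × ULN and stays there is counted in the same cell as a subject who reached that grade on study. The table cannot separate abnormality due to disease or background drug from abnormality that arose after the additions.

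**Working it through.** The plan gives no figure on this point, so there is none to reproduce. The check concerns what the counting rule does.

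**1. Can subjects enter with an abnormal value?** Yes.
- ALT, AST and bilirubin may exceed ULN at entry, so they may be out of range by definition.
- Hemoglobin has no limit.
- For ANC and platelets, the entry floors (1.0 and 50 × 10⁹/L) lie below the levels required for complete response in Section 10.4 (above 1.5, and at least 100 × 10⁹/L). Those are response criteria, not reference ranges, but they show that the protocol regards counts between the two as not recovered.
- Section 9.5.2.1 reports Grade 3 or 4 neutropenia in 98/240 = 41% of subjects on venetoclax. This is not a baseline prevalence here; it only makes pre-existing cytopenia plausible.

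**2. Where is the mixing confined?** Section 4 requires eligibility at screening and again on Cycle 1 Day 1 before dosing. A later ANC below 1,000 or platelet count below 50,000 is therefore a fall from entry. For these two counts, mixing can occur only at or above the floors. Hemoglobin has no such bound. The documents do not reproduce the CTCAE cut-offs, so the floors are not translated into grades here.

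**3. How likely is an unchanged mild abnormality to be counted?** The schedule in Section 7.1 gives 3 (Cycle 1 Days 2, 8, 15) + 5 (Cycles 2 to 6) + 6 (Cycles 9 to 24, every third) = 14 post-baseline hematology draws for a subject treated through Cycle 24. If each draw is abnormal with probability p, and draws are treated as independent (an assumption), the chance of at least one is 1 − (1 − p)¹⁴: 77% for p = 10%, 96% for p = 20%, and above 99.9% for p = 50%.

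**4. How large is the excess?** Let q be the proportion abnormal at baseline, and e the proportion who become abnormal or worsen in grade, taken as equal in subjects normal and abnormal at entry. Assume that every subject abnormal at entry has at least one abnormal value later.
- Planned any-grade incidence: q + (1 − q)e
- Baseline-adjusted incidence: e
- Excess: q(1 − e)

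Neither q nor e is in the documents. Assumed ranges give:

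| q | Planned, e = 0 | Planned, e = 20% | Planned, e = 40% | Excess at e = 0 / 20% / 40% (points) |
|---|---|---|---|---|
| 10% | 10% | 28% | 46% | 10 / 8 / 6 |
| 20% | 20% | 36% | 52% | 20 / 16 / 12 |
| 30% | 30% | 44% | 58% | 30 / 24 / 18 |
| 50% | 50% | 60% | 70% | 50 / 40 / 30 |

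In whole subjects, with about 28 per cohort: if 8 enter abnormal and nobody worsens, the planned table shows 8/28 = 28.6% (Clopper-Pearson 95% CI 13.2% to 48.7%). A worsening rule shows 0/28 (0% to 12.3%).

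**The case against.** A reader might infer that the plan reports entry cytopenias as toxicity of the triplet. The documents do not support that. Section 12.5.2 calls the entries abnormal results and attributes no cause. Causality is assessed for adverse events (Section 12.5), and Sections 12.4 and 12.9.5 bring worsening into those tables. A laboratory value becomes an adverse event only if it is tied to overdose or hospitalization or is judged clinically significant. Section 8.4 also separates cytopenias due to disease from those due to study drug. An unchanged low count does not become drug toxicity merely by appearing in the laboratory table.

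Other parts of the defense also stand. Change from baseline is tabulated in the same paragraph. The any-post-baseline table over-counts rather than hides abnormality, and it describes how common abnormal values are on treatment. It is split by grade, and for ANC and platelets the values below the entry floors are real falls. The assumed prevalences say nothing about the actual size in this trial.

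None of this closes the gap. By-visit summaries of change do not show how many subjects moved up a grade. Entry to the adverse event tables depends largely on investigator judgment. The graded table is the one systematic subject-level laboratory count that does not, and it lacks a baseline rule.

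**Conclusion.** The point holds in a limited form. Followed as written, Section 12.5.2 produces a graded incidence that combines abnormalities present at entry with new or worsened ones, and no planned display separates them by subject and grade. For ANC and platelets this is confined to values at or above the entry floors.

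The size cannot be established, because the documents give neither baseline prevalence nor reference ranges. The excess is q(1 − e) under the stated assumptions: equal e in both groups, and at least one later abnormal value in every subject abnormal at entry. The tabulated 6 to 50 points are a range over assumed inputs, not an estimate for this trial, and they apply to any-grade incidence.

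The consequence is for interpreting the secondary safety objective. The primary endpoint and its analysis are unaffected.

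**What to change.** In Section 12.5.2, add for each laboratory parameter and cohort:

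- a shift table of baseline grade by worst post-baseline grade;
- an incidence of treatment-emergent abnormality, counting a subject when the grade exceeds that of the baseline value.

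Define baseline as the last value before the first dose on Cycle 1 Day 1. The footnotes to Section 7.1 require that day's assessments before dosing, so a Day 1 sample qualifies.

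Keep the any-post-baseline table, labelled as not adjusted for baseline, and keep the by-visit summaries.

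The cost is analysis wording and a few extra tables. Hematology and chemistry are already scheduled at screening, on Cycle 1 Day 1 and throughout treatment, so no new sample or visit is needed.
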